6.2. Exclusion Criteria

A documented diagnosis, or the patient reports any, of the following:

- Current use of any of the trial interventions or has used any within the last 12 weeks*#.
 Patients can continue any other treatment modality they currently find helpful for their TMD subject to no absolute contraindications to its use alongside the interventions under investigation.
- 2. Any other subtype of TMD that is the primary cause of familiar pain detected on clinical examination; familiar pain is pain provoked by clinical exam or testing/movement of a structure that matches the patient's primary complaint e.g., for M-TMD familiar pain is provoked from examination or use of the muscles of mastication. Patients can have other forms of (painful) TMD comorbid with M-TMD, but these should not be the primary cause of familiar pain determined by DC/TMD derived diagnostic procedures.
- 3. Enrolled in another interventional research trial which could affect the outcome of this trial.
- 4. People who are pregnant, planning pregnancy, or breast-feeding during the time of the trial participation*.
- 5. Current or planned acupuncture within trial period or 3 months prior to trial period*.
- 6. Formal diagnosis of lactose intolerance or lactose allergy and unable / unwilling to receive oral capsules of lactose free gabapentin if randomised to the treatment as usual arm**.
- 7. Fibromyalgia
- 8. Neuropathic pain
- 9. Coagulopathy
- 10. Uncontrolled hyperthyroidism
- 11. Renal failure
- 12. Severe liver disease
- 13. Connective tissue disorders e.g. Ehlers-Danlos syndrome, Epidermolysis bullosa, Marfan syndrome, Osteogenesis imperfecta, Rheumatoid arthritis, Poly/dermatomyositis, Scleroderma, Sjogren's syndrome, Systemic lupus erythematosus, Vasculitis
- 14. Any (previous) substance use disorder
- 15. Concerns from the research or clinical team over patient safety due to psychosocial distress, previous or current mental health illness*
- 16. Taking any of the following groups of medications:
 - a. Aminoglycoside antibiotics
 - b. Anticholinesterases
 - c. Non-depolarising and depolarising muscle relaxants
 - d. Opiates other than codeine. If taking codeine (including co-codamol), please see footnote†
 - e. Monoamine oxidase inhibitors (MAOIs)
- 17. Allergy or intolerance to any trial intervention, or any contraindication as per each IMP SmPC
- 18. For the MRI sub study group:

- a. cardiac pacemaker, defibrillator or pacing wires.

 - For any other formulation of codeine, if its dosage ≥ 30mg in a singular ingestion or more frequently than every 4 hours, a principal investigator led risk assessment should be conducted and recorded, to ensure that if the patient was to receive Treatment As Usual there are no other are no other sedative drugs e.g. benzodiazepines, z-drugs etc or other comorbidities that might place the patient at greater risk of respiratory depression or challenges e.g. diminished respiratory function or sleep apnoea. If there are any concerns, the patient will not be eligible for the trial
 - No other type of opiate, other than codeine dosing as referred to above, is allowed on trial entry

^{*}If the chronology of events allows, the potentially eligible patient can be booked to be rescreened for a place on the trial at an appropriate point in the future.

All codeine use, at trial entry and during the trial, must be recorded in medications section of CRF

6.3. Effective Methods of Contraception

As per the MHRA's Clinical Trials Facilitation Group, for the purposes of the protocol a woman is considered of childbearing potential (WOCBP), i.e. fertile, following menarche and until becoming post-menopausal unless permanently sterile. Permanent sterilisation methods include hysterectomy, bilateral salpingectomy and bilateral oophorectomy. The protocol also acknowledges that a person of child-bearing potential is defined as either a cis-female or trans-male. Individuals able to help achieve conception are defined as either cis-male or trans-female.

For the purpose of this protocol, a man is considered fertile after puberty unless permanently sterile by bilateral orchidectomy.

To be eligible for the trial, participants of child-bearing potential who are sexually active must confirm that they understand the need to use a highly effective method of contraception (failure rate of <1%) for the duration of their involvement of the trial. Participants of child-bearing potential must also confirm that they understand that any sexual partner capable of helping them conceive should also use a highly effective method of contraception during involvement in the trial. Those sexual partners must also confirm that they understand they need to use a highly effective method of contraception for the duration of the trial. Barrier methods are not considered highly effective and female partners of male participants are also advised to use a highly effective method of contraception additionally. Similarly, the reverse is true for any participant who can help achieve conception with sexual partner(s) of childbearing potential.

Highly effective methods include:

Persons of child-bearing potential	Partners of trial participants able to help achieve conception
 Combined (estrogen and progesterone containing) hormonal contraception associated with inhibition of ovulation (oral, intravaginal, transdermal) Progesterone-only hormonal contraception associated with inhibition of ovulation (oral, injectable, implantable) Intrauterine device (IUD) Intrauterine hormone-releasing system (IUS) Bilateral tube occlusion or hysterectomy Vasectomised partner (>3 months earlier) Sexual abstinence 	 Condom Sexual abstinence Vasectomy or vaginoplasty/genital reconstruction permanently sterile by bilateral orchidectomy

Abstinence is defined as refraining from sexual intercourse with the potential for conception. Abstinence is acceptable only as true abstinence: when this is in line with the preferred and usual

MiTiGate Clinical trial protocol IRAS ID: 1008152

lifestyle of the patient. Periodic abstinence (e.g., calendar, ovulation, symptothermal, post-ovulation methods), assumption of no conceptive potential (excepting amenorrhea detailed below), and withdrawal are not acceptable methods of highly effective contraception for the purposes of the trial.

Participants are postmenopausal, when they have had no menses for 12 months without an alternative medical cause. A high follicle stimulating hormone (FSH) level in the postmenopausal range may be used to confirm a post-menopausal state in women not using hormonal contraception or hormonal replacement therapy. However, in the absence of 12 months of amenorrhea, a single FSH measurement is insufficient and a second measurement must confirm this.

Applicable contraceptive methods should be recorded in the participant's medical record.

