6.1. Inclusion Criteria

- 1. Adults ≥18 years old
- 2. Willing and able to give informed consent prior to trial procedures occurring.
- 3. DC/TMD (Schiffman et al., 2014) derived diagnosis of M-TMD with pain for ≥3months identified as the primary complaint of familiar pain.
- 4. Self-management trialled for ≥6 weeks and not controlled the pain to the patient's satisfaction*
- 5. Minimum pain intensity of 30 on CPI over last 3 months (Dworkin et al., 2010; Von Korff et al., 1992)
- 6. For people of childbearing potential: an agreement to use a highly effective method of contraception or to practise sexual abstinence to avoid pregnancy for the duration of trial involvement. Refer to section 6.3.
- * Self-management is defined as comprising any, or a combination of the following international agreed components: education, self-exercise therapy, thermal modalities, self-massage therapy, dietary/nutrition advice, or parafunctional activity identification, monitoring, and avoidance (Durham et al., 2016a). If a patient has yet to complete 6 weeks but is eligible on all other criteria for the trial it is permissible, to arrange to rescreen them following the completion of self-management. In self-referrals to the trial who have yet to complete 6 weeks and require further information: these patients can be signposted to the freely available standardised self-management information produced in collaboration with the lead site and co-produced with patients for ease of understanding (https://www.tims.nhs.uk/wp-content/uploads/2020/06/4.5-TIMS-TMD.pdf and https://www.newcastle-hospitals.nhs.uk/services/facial-pain/#temporomandibular-disorder-tmd and asked to discuss with their general dental practitioner). They can then be re-screened for the trial pending their review at 6 weeks.

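### Section 6.3 rules barrier methods out as highly effective contraception, then lists condom as a highly effective method for partners

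*Protocol*

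**What the plan says.** Inclusion criterion 6 (Protocol section 6.1) asks people of childbearing potential for "an agreement to use a highly effective method of contraception or to practise sexual abstinence to avoid pregnancy for the duration of trial involvement", and refers to section 6.3 for the detail.

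Section 6.3 sets out what has to be understood before entry, in a paragraph framed as a condition of eligibility:

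- Sexually active participants of child-bearing potential have to confirm their awareness of this: "the need to use a highly effective method of contraception (failure rate of <1%) for the duration of their involvement of the trial".
- Their confirmation covers partners too, in these words: "any sexual partner capable of helping them conceive should also use a highly effective method of contraception during involvement in the trial".
- The partners have a confirmation of their own: "Those sexual partners must also confirm that they understand they need to use a highly effective method of contraception for the duration of the trial".
- On barrier methods the paragraph says: "Barrier methods are not considered highly effective".

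A two-column table follows, introduced by "Highly effective methods include". The first column is for persons of child-bearing potential. The second is headed "Partners of trial participants able to help achieve conception", and its entries are condom, sexual abstinence, vasectomy or vaginoplasty/genital reconstruction, and permanent sterility by bilateral orchidectomy.

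Section 7.1.2 (Consent) describes the method that must be re-explained at the screening visit as acceptable and effective, not as highly effective, and also points to section 6.3.

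**The concern.** A condom is a barrier method. Section 6.3 therefore both denies and grants it the status of a highly effective method, within a few lines. Site staff who explain the partner requirement from the prose will say that a condom does not meet it. Staff who work from the table will say that it does. Both will be following the current protocol.

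What is at stake is that participants and partners at different sites may be told different things about a safety measure that they are asked to confirm they understand. Pregnancy is an exclusion and a listed reason for withdrawal, and it must be reported within 24 hours, so the contraception wording has a working role in the trial. The schedule of events places dipstick pregnancy tests only at screening and week 36. Between those two points the protocol relies on the contraception advice.

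**Working it through.** No arithmetic applies. The check is a comparison of the statements in section 6.3, and of that section with the places that refer to it.

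**Step 1. The standard.** The <1% failure rate is attached to the term highly effective in the sentence on participants. The sentences on partners use the same term without a second definition, so the same standard is taken to apply to them.

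**Step 2. Prose against table.**

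| Question | Prose of 6.3 | Table in 6.3 |
|---|---|---|
| Must the partner's method be highly effective? | Yes | Yes: the lead-in covers both columns |
| Is a barrier method highly effective? | No | Partner column: yes, condom is listed |
| Is a barrier method offered for the participant's own use? | No | No: the participant column has none |

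Only the second row conflicts, and only for partners.

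**Step 3. Is the condom entry qualified?** It has no footnote, and the lead-in makes no distinction between columns. Nothing in the table says that condom is only an added measure.

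**Step 4. How far apart are the two readings?** Without condom, the partner column contains only abstinence and surgical or permanent sterility. If the prose governs, a partner who is neither abstinent nor sterile has no listed option that qualifies. If the table governs, a condom is enough. The two readings give different instructions for such partners.

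**Step 5. Does the conflict reach criterion 6?** Criterion 6 tests the participant's own agreement to a highly effective method or abstinence. Prose and participant column agree on what that means, so this obligation is consistent. The partner clause does sit in the eligibility paragraph, but what it demands is confirmed understanding, not proof of which method the partner uses.

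**Step 6. Does another section resolve it?** Section 6.1 refers back to 6.3. Section 7.1.2 also refers back to 6.3 and uses a weaker description of the method. Neither states whether a partner's condom use meets the requirement.

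**The case against.** The strongest defence is that the partner's measure comes on top of the participant's own method. On either reading, a sexually active participant of child-bearing potential must already use a method with a failure rate below 1%, so the ambiguity touches only a second layer of protection. The sentence on barrier methods goes on to advise female partners of male participants to use a highly effective method in addition, which suggests that condom was meant as a supplement. Section 6.3 also requires the methods in use to be recorded.

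Most of this stands, and it limits how much weight the point can bear. It does not remove the contradiction: the table presents condom as highly effective without qualification, and a site has to guess at the intended meaning.

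Two stronger readings are tempting, and the documents support neither.

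- A reader might infer that one participant could pass eligibility under the table and fail under the prose, and so, because section 6 treats enrolling someone who does not meet the criteria as a breach and permits no waivers, that enrolments are at risk. This does not follow. Criterion 6 is consistent for the participant, and someone who confirms understanding of the partner requirement meets the wording of that clause whatever the partner uses. No criterion can be named that the condom entry causes a participant to fail.
- A reader might infer that a large share of participants is affected, since section 1 says that first onset of TMD peaks in the fourth decade. That is a statement about onset of TMD in general. It gives neither the age, sex and partner status of this trial's population nor the use of condoms in it.

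**Conclusion.** Section 6.3 contradicts itself on whether a barrier method meets the contraception requirement for partners. The contradiction is in current text, both table columns are legible, and nothing else in the protocol resolves it.

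The point is minor. It concerns one entry in one column and the partner requirement that participants and partners must confirm they understand. No number affected can be derived, and there is no consequence for the estimand, sample size, power, type I error or analysis. It is still worth correcting, because this is an operative safety instruction that sites cannot follow in both forms.

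The conclusion rests on two readings of the text: that a condom is a barrier method, and that the term highly effective has one meaning throughout section 6.3. It takes no position on which rule is clinically right.

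**What to change.** Reconcile the prose of section 6.3 with the partner column of its table so that a single statement on barrier methods applies. The sponsor decides which rule holds. Whichever is chosen, the table lead-in, the column heading and the status of the condom entry should say the same thing as the prose.

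Align the description of the required method in section 7.1.2 with the reconciled section 6.3. Criterion 6 needs no rewording, since it already refers there. The eligibility checklist and participant information sheet are not among the documents reviewed; the sponsor should check whether either repeats the conflict.

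The cost is wording in a protocol amendment, and in the participant information sheet if it carries the same text. No change to data collection, sample size or analysis is needed.

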7. TRIAL PROCEDURES

7.1. Recruitment

This is a multicentre trial recruiting from at least 12 secondary care centres in the United Kingdom. 663 participants will be recruited for this trial from one of three entry points:

- a) Secondary care identification of patient under their care who fits the criteria.
- b) Primary care referral of patient to trial who they believe fits the criteria.
- c) Self-referral following public advertisement of the trial.

7.1.1. Patient Identification

Primary care and secondary care participants will be identified by either attendance at routine clinics (including outreach dental screening clinics), records/database search, or self-referral to the trial in response to public advertisements, including those on social media at its email address ([contact]). Patients may also self-refer to local sites if appropriate.

The trial will use a short verbal explanation of the trial and/or a standard letter of invitation as appropriate, followed by a participant information sheet (PIS) to approach those potentially eligible for the trial. This may be in person at a routine clinic appointment, or by post, phone, videoconference, or email as appropriate to the method of identification of the potential participant.

For all identification methods except self-referral the patient's regular clinical care team will request permission from the potentially eligible participant for the research team to contact them (where the regular clinical care team is not the same as the research team). Where the patient is in primary care, permission will be sought from the patient to refer them to the research team at the local trial site.

Self-referral to the trial will be encouraged through public advertisements, word of mouth, social media and use of other public fora and media. The advertised self-referral process will explain people may be eligible to self-refer if they:

• can answer yes to both of the two most sensitive and specific screening questions for TMD (Lövgren et al., 2016; Nilsson et al., 2006) − 1) Do you have pain in your temple, face, jaw or

jaw joint once a week or more, and 2) Do you have pain once a week or more when you open your mouth or chew?;

- have had the pain for 3 months or greater; and
- have tried self-management for at least 6 weeks.

Those then self-referring to the trial will do so through its email address ([contact]), or via a local secure site email address, when appropriate, by confirming they can answer in the affirmative to the specific two screening TMD questions (Nilsson 2006; Lovgren et al 2016). An initial contact will then be made by clinical members of the Newcastle research team, or the local research team, by sending a standard email/letter of invitation and PIS to them. A follow-up expression of interest call will be scheduled with clinical members of the research team (Newcastle team or local site) approximately a week later to answer any questions patients have and confirm their demographics and TMD status, including treatment. If they are interested in participating, have a high likelihood of being eligible for the trial, and have a site near them, then they can be invited to attend a screening visit at their nearest site. If at any point during the self-referral process a potential participant's details need to be transferred to their local site, they will be asked for permission to securely send their details to that site so they can be invited to attend a screening visit at their nearest site

7.1.2. Consent

Those potentially eligible for the trial will be invited to a screening visit (visit 1) where informed consent will be taken. Screening will occur at the secondary care site either within a normal scheduled clinic visit or at a research specific visit. Potential participants will have had sufficient time to review the trial documentation at this visit; this will likely be at least 24 hours but may be less in some circumstances. For example, a potential participant would like to be screened at same routine clinic visit as the approach is made to participate in the trial once they have considered the information on the trial and have had any questions that they may have had answered to their satisfaction. During, and prior to, the screening visit (visit 1) potential participants will be given opportunity, and encouraged, to ask questions about the trial given they will have received the PIS and a description of the trial. At the screening visit the following will be re-explained:

- a) How the trial will run and its duration.
- b) Their right to withdraw at any time by revoking their consent without any detriment to them.
- c) For people of childbearing potential, the need for an acceptable effective method of contraception or to practise sexual abstinence (see section 6.3).
- d) The common adverse effects associated with the trial interventions.
- e) The likelihood of Botulinum toxin not immediately being available through routine NHS treatment at the end of the trial.

Informed consent will be sought by an appropriately trained and clinically qualified member of the research team who is delegated to do so at that site. For non-English language speakers or those with additional communication needs there will be appropriate professional interpretation or technical

services employed in line with the local site's policies and protocols. Relatives **are not to be used** to interpret for the potential participant.

Written informed consent will be taken before any of the screening activities are undertaken as part of the screening visit (Visit 1). Consent will be documented in the individual's clinical notes and include confirmation of a-e above and the following details:

- Date the potential participant received the PIS.
- Date and version of PIS used, and consent form used.
- A brief summary of any questions asked by the potential participant and the answer(s) given.

The original copy of the signed consent form will be retained in the Investigator Site file (ISF) with additional copies being provided to the participant and a copy scanned or placed into their clinical notes in secondary care. Participants will give specific permission for their GP and general dental practitioner/referring clinician and relevant consultant (where applicable) being informed of their trial participation.

In the event of protocol amendments or information becoming available that might affect the participant's willingness to continue in the trial it may become necessary to re-consent the participant. This would be completed on an updated consent form after all necessary approvals are obtained.

7.1.3. Screening and eligibility assessment

Screening will occur following written informed consent and before randomisation. All potential participants will be screened and clinically reviewed and examined to assess eligibility and ensure compliance with trial inclusion and exclusion criteria (sections 6.1 & 6.2).

Each potential participant will be assigned a unique Subject ID number to identify them, which at the point of randomisation will then become their Subject ID for the trial. Everyone considered for the trial, including those who fail screening, must be recorded on the electronic trial screening database. The Subject ID number will be a six-digit code and used within the trial database and all other relevant documents. If a potential participant does not go on to be randomised the Subject ID will not be reused.

Eligibility will be assessed at the site by a clinician appropriately delegated to do so by the site PI and the assessment will be documented in the participant's clinical (e-) notes, which includes a statement of eligibility. An eligibility checklist will be completed in the clinical data management system (CDMS) for all patients screened for the trial.

The patient will be informed whether they meet eligibility criteria and treatment arranged as necessary. Patients who do not meet the eligibility criteria will continue with their standard treatment pathway with their original care team and will be considered as 'screen failures'. These 'screen failures' will be recorded on the screening log with reasons for not participating in the trial documented wherever possible. Screen failures **do not** count towards recruitment targets. An

electronic screening log, integrated into the Sealed Envelope Redpill database will capture anonymised screening data, when available, including:

- Patient referral method to trial: NHS clinic, self-referral, primary care dental, primary care medical
- Number of patients referred to, or approached, by trial sites and provided with a PIS.
- The number of patients eligible/not eligible and reasons (e.g. not diagnosed with M-TMD).
- Potentially eligible patients approached for consent.
- Patients declined/not consented and the reasons why (if known).
- Patients deemed ineligible at screening may be rescreened at a later date if there is a change
 in circumstances and the trial has not closed to recruitment.

The other data collection at the screening and eligibility assessment are described in section 7.4.

